- 7. Patient has adequate bone marrow and organ function as defined by ALL of the following laboratory values (as assessed by local laboratory):
 - Absolute neutrophil count $\geq 1.5 \times 10^9/L$
 - Platelets $\geq 100 \times 10^9/L$
 - Hemoglobin $\ge 9.0 \text{ g/dL}$
 - Potassium, sodium, calcium corrected for serum albumin and magnesium within normal limits or corrected to within normal limits with supplements before first dose of the study medication
 - INR ≤ 1.5
 - Serum creatinine < 1.5 mg/dl or creatinine clearance ≥ 50 mL/min
 - In absence of liver metastases, alanine aminotransferase (ALT) and aspartate aminotransferase (AST) should be below $2.5 \times ULN$. If the patient has liver metastases, ALT and AST should be $< 5 \times ULN$.
 - Total bilirubin < ULN except for patients with Gilbert's syndrome who may only be included if the total bilirubin is $\leq 3.0 \times$ ULN or direct bilirubin $\leq 1.5 \times$ ULN
- 8. Patient must have a 12-lead ECG with ALL of the following parameters at screening:
 - QTcF interval at screening < 450 msec (using Fridericia's correction)

- Resting heart rate \geq 50 bpm
- 9. Patient must be able to swallow ribociclib and letrozole tablets
- 10. Patient has signed informed consent obtained before any trial-related activities and according to local guidelines
- 11. Patients must be able to communicate with the investigator and comply with the requirements of the study procedures

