6.1 Study treatment

For this protocol, the term "investigational drug" refers to the Novartis study drug ribociclib. The other drugs to be used in this study are letrozole and either goserelin or leuprolide (for men / premenopausal women). "Study treatment" in this protocol refers to the combination of drugs and includes investigational drug (ribociclib) as well as letrozole and goserelin or leuprolide (if applicable).

Ribociclib will be supplied by Novartis or its designee as 200 mg tablets as individual patient supply packaged bottles. Letrozole (Femara or generic equivalent), goserelin and leuprolide will be procured locally by Country Pharma Organization or local institution as it is commercially available in each participating country according to local practices and regulations. Storage conditions are described in the medication label. Medication labels will comply with the legal requirements of each country and be printed in the local language.

All dosages prescribed and dispensed to the patient and all dose changes during the study must be recorded on the Dosage Administration Record in the eCRF.

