6.1.1 Dosing regimen

Ribociclib (LEE011) will be given orally once a day on days 1-21 of each 28- day cycle. On days 22-28 ribociclib will not be given ("rest days"). Letrozole will be given orally as per SmPC once a day on a continuous daily schedule (days 1-28 of each 28- day cycle). There will be no "rest" in the letrozole schedule. For men and premenopausal women, either goserelin will be given as an injectable subcutaneous implant or leuprolide will be given as an intramuscular injection. Either goserelin or leuprolide is recommended to be administered on day 1 starting at Cycle 1 and then every 28 days. Goserelin or leuprolide must be given as the monthly injection dosage form, as the 3-month depot dosage forms do not reliably suppress hormonal levels in all patients (NCCN ver. 2 2017). If a patient is already receiving goserelin or leuprolide before C1D1, a 28 days schedule should be maintained based on the pre-existing dosing schedule.

Table 6-1 Dose and treatment schedule			
Study treatments	Pharmaceutical form and route of administration	Dose	Frequency and/or Regimen
Ribociclib	Tablet for oral use	600 mg (3 tablets of 200 mg)	Daily on D1-D21 (28 day cycles)
Letrozole	Tablet for oral use	2.5mg	Continuous Daily
Goserelin	Injectable Subcutaneous implant	3.6 mg	Every 28 days (only for men and premenopausal women)
Leuprolide	Injectable Intramuscular Depot	7.5 mg	Every 28 days (only for men and premenopausal women)

See Table 6-1 and Figure 6-1 for details.

Figure 6-1 Men / Premenopausal regimen

* One cycle is 28 days unless modified due to AEs

Figure 6-2 Postmenopausal regimen

* One cycle is 28 days unless modified due to AEs

The study treatment will be administered as a flat-fixed dose (Starting doses: Ribociclib 600 mg QD 3 weeks on/1 week off; letrozole 2.5 mg QD continuously), and not by body weight or body surface area.

The investigator or responsible site personnel should instruct the patient to take the study treatment as per protocol (emphasizing the importance of compliance). Drug accountability must be performed on a regular basis. Patients will be instructed to return unused study treatment to the site at the end of each cycle. The site personnel will ensure that the appropriate dose of each study treatment is provided at each visit.

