6.3.1.3.3 Additional follow-up for QTc prolongation

- Assessing cardiovascular dysfunction or impaired liver oxygenation, including hypotension or right heart failure as possible etiologies for liver dysfunction.
- Consider a liver biopsy as clinically indicated to assess pathological change and degree of potential liver injury

All cases of DILI confirmed on repeat testing meeting the laboratory criteria defined above, with no other alternative cause for LFT abnormalities identified, should be considered as "medically significant", thus meeting the definition of SAE (Section 8.2.1), and must be reported as SAE using the term "potential drug-induced liver injury". All events must be followed up with the outcome clearly documented. Results of tests as well as other clinically important information will be recorded in the eCRF.

Grade	Dose Modification	
For All Grades	1. Check the quality of the ECG and the QT value and repeat if needed.	
	 Perform analysis of serum electrolytes (K+, Ca++ correct for albumin, Phos, Mg++). If outside of the normal range, interrupt ribociclib administration, correct with supplements or appropriate therapy as soon as possible, and repeat electrolytes until documented as normal. 	
	 Review concomitant medication usage for the potential to inhibit CYP3A4 and/or to prolong the QT interval. 	
	4. Check compliance with correct dose and administration of ribociclib.	
1 QTcF 450-480 ms	Perform steps 1-4 as directed in "For All Grades." No dose adjustment required.	
2	Interrupt ribociclib. Perform steps 1-4 as directed in "For All Grades."	
QTcF 481-500 ms	Perform a repeat ECG within one hour of the first QTcF of \geq 481 ms.	
	Repeat ECG as clinically indicated until the QTcF returns to < 481 ms. Restart ribociclib with dose reduced by 1 dose level. Refer to Table 6-2 for dosing schedule.	
	If QTcF \ge 481 ms recurs, ribociclib should be reduced again by 1 dose level.	
	Repeat ECG 7 days and 14 days after dose resumption (then as clinically indicated) for any patients who had therapy interrupted due to $QTcF \ge 481$ ms	
3	Interrupt ribociclib. Perform steps 1-4 as directed in "For All Grades."	
QTcF ≥ 501 ms on at least	Perform a repeat ECG within one hour of the first QTcF of \geq 501 ms.	
two separate ECGs	If QTcF remains \ge 501 ms, consult with a cardiologist (or qualified specialist) and repeat cardiac monitoring as indicated until the QTcF returns to < 481 ms.	

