	 If QTcF returns to < 481 ms, ribociclib will be reduced by 1 dose level. Refer to Table 6-2 for dosing schedule. 	
	• If QTcF remains ≥ 481 ms after performing steps 1-4 as directed in "For All Grades," discontinue ribociclib.	
	Repeat ECG 7 days and 14 days after dose resumption (then as clinically indicated) for any patients who had therapy interrupted due to $QTcF \ge 501$ ms If $QTcF$ of ≥ 501 ms recurs, discontinue ribociclib.	

Table 6-5 Ribociclib dose adjustment and management recommendation for QTcF prolongation

Grade	Dose Modification
4 [QT/QTcF ≥ 501 or > 60 ms change from baseline] and [Torsades de pointes or polymorphic ventricular tachycardia, or signs/symptoms of serious arrhythmia]	 Discontinue ribociclib. Perform steps 1-4 as directed in "For All Grades." Obtain local cardiologist (or qualified specialist) consultation and repeat cardiac monitoring as indicated until the QTcF returns to <481 ms.

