7.2.2.6 Cardiac assessments

7.2.2.6.1 Electrocardiogram (ECG)

Standard 12 lead ECG assessments will be performed locally at screening, C1D15, C2D1, and thereafter as clinically indicated, and EOT visit (see Table 7-1). There will be no central review of ECGs. QT interval corrected by Fridericia's formula (QTcF) will be used in this trial for trial eligibility and safety assessments.

If an abnormal ECG or QTcF value of \geq 481 ms is obtained at any time after C1D1, study treatment must be interrupted, repeat ECG and follow management guidelines detailed in Table 6-5.

An unscheduled ECG may be repeated at the discretion of the investigator at any time during the study and as clinically indicated. Local cardiologist ECG assessment may be performed at any time during the study at the discretion of the investigator.

Interpretation of the tracing must be made by a qualified physician and documented on the ECG eCRF page. Each ECG tracing should be labeled with the study number, patient initials (where regulations permit), patient number, date, and kept in the source documents at the study site. Clinically significant abnormalities present when the patient signed informed consent should be reported on the Medical History eCRF page. Clinically significant findings must be discussed with Novartis prior to enrolling the patient in the study. New or worsened clinically significant findings occurring after informed consent must be recorded on the Adverse Events eCRF page.

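### Protocol 7.2.2.6.1 orders interruption of all study treatment for an abnormal ECG or QTcF of 481 ms or more, while the table it cites interrupts ribociclib only and requires no dose adjustment at 450–480 ms

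*Protocol*

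**What the plan says.** The ECG section (Protocol 7.2.2.6.1) schedules tracings as follows: "Standard 12 lead ECG assessments will be performed locally at screening, C1D15, C2D1, and thereafter as clinically indicated, and EOT visit". Its action rule opens with "If an abnormal ECG or QTcF value of" at least "481 ms is obtained at any time after C1D1, study treatment must be interrupted, repeat ECG and follow management guidelines detailed in Table 6-5".

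Protocol 6.1 defines study treatment as the combination, which "includes investigational drug (ribociclib) as well as letrozole and goserelin or leuprolide (if applicable". The same section keeps a separate term, investigational drug, for ribociclib alone. SAP 2.1.3 draws the same distinction.

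Table 6-5, in Section 6.3.1.3.3, is a ribociclib table by title and content. At Grades 2 and 3 it begins "Interrupt ribociclib. Perform steps 1-4 as directed in" its all-grades steps. At Grade 4 it discontinues ribociclib. At Grade 1 (QTcF 450–480 ms) it asks for the all-grades checks and no dose adjustment. It gives no instruction to hold letrozole or the LHRH agonist. Section 6.4.4 cites this table and also names ribociclib as the drug to interrupt.

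On the partner drugs, Section 6.1.1 states: "Letrozole will be given orally as per SmPC once a day on a continuous daily schedule". It adds that the letrozole schedule has no rest period. Sections 6.3.1.1 and 6.3.1.2 plan no dose modification of letrozole, goserelin or leuprolide.

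**The concern.** One mandatory sentence gives two instructions that do not match. The first, through the Section 6.1 definition, stops every component of the regimen. The second sends the site to a table that stops one component.

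A site that follows the first instruction literally holds letrozole, contrary to the continuous schedule. For a man or premenopausal woman it also holds any goserelin or leuprolide injection that falls due. The scheduled C2D1 ECG falls on the day the second injection is due for patients who started the LHRH agonist at C1D1. A site that follows only the table departs from the literal wording of 7.2.2.6.1. Section 12 permits no authorized deviations, so the text should not put sites in this position.

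The second problem is the trigger. The protocol does not define an abnormal ECG, yet the phrase carries a mandatory interruption. Tracings are read locally without central review, so sites could apply it differently.

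**Working it through.** No sample size, power or error rate is involved. The check is a comparison of texts.

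**Which drugs are interrupted**

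| Place | Drug(s) | Instruction |
|---|---|---|
| 7.2.2.6.1 | Study treatment | Interrupt |
| 6.1; SAP 2.1.3 | Study treatment means ribociclib + letrozole + goserelin/leuprolide if applicable | Definition |
| Table 6-5, Grades 2 and 3 | Ribociclib | Interrupt |
| Table 6-5, Grade 4 | Ribociclib | Discontinue |
| 6.4.4, citing Table 6-5 | Ribociclib | Interrupt |
| 6.1.1 | Letrozole | Continuous, no rest |
| 6.3.1.1, 6.3.1.2 | Letrozole; goserelin/leuprolide | No dose modification planned |

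The statements in 6.3.1.1 and 6.3.1.2 do cover interruptions, because Section 6.3.1 counts interruptions and reductions together as dose modifications. The wording of 7.2.2.6.1 therefore conflicts with the table it cites and with the dosing sections.

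**Where the trigger starts**

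- The numerical thresholds agree: 481 ms in 7.2.2.6.1, and Table 6-5 Grade 2 starts at 481 ms.
- The abnormal-ECG limb has no threshold. QTcF 450–480 ms can fairly be called abnormal: entry requires "QTcF interval at screening < 450 msec", Table 6-5 grades the range, and SAP 2.8.5.1 tabulates new values above 450 and up to 480 ms as notable.
- Read that way, 7.2.2.6.1 interrupts treatment at 450–480 ms. Table 6-5 Grade 1 requires no dose adjustment there, apart from a ribociclib hold if the all-grades electrolyte check is out of range.
- That reading would also make the 481 ms figure in the same sentence redundant, so it is unlikely to be intended.
- A finding already present at screening and of no clinical importance would also meet the trigger at every later ECG.

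**How many patients could meet the QTcF part**

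Protocol 1.2.1.2.1 reports QTcF above 480 ms in 3.3% of the ribociclib arm of MONALEESA-2. Amendment 04 reports 3,246 treated patients. If that rate carried over, 0.033 × 3,246 = 107.1, or about 107 patients. The documents give no rate for the abnormal-ECG limb.

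**Effect on counts**

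At QTcF of 481 ms or more, ribociclib is interrupted under either text. The number of patients with a ribociclib interruption is therefore unchanged, and so is their entry in the primary-endpoint category for adverse events leading to dose reduction or interruption.

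**The case against.** The strongest reply is that few sites would misread the rule. The same sentence sends the reader to a table titled for ribociclib dose adjustment, Section 6.4.4 names ribociclib, and Section 6.3.1.3 manages severe reactions by changing ribociclib. A qualified physician must interpret each tracing, and Sections 6.3.1 and 6.3.1.3 leave management to clinical judgement except where discontinuation is mandated. This stands as evidence of intent and is the reason the point is minor. It does not make the sentence correct: the protocol has a ribociclib-only term and did not use it here, and Table 6-5 nowhere says that the other drugs continue.

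A reader might infer more than the documents support:

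- **A long loss of letrozole.** One could assume that the letrozole hold lasts as long as the ribociclib hold and compute a fall in dose intensity. Nothing sets that duration. Table 6-5 asks for a repeat ECG within one hour at Grades 2 and 3 and, once it governs, gives no reason to keep letrozole on hold. A delay to the C2D1 injection is uncertain for the same reason.
- **A missing rule for serious arrhythmia below 481 ms.** Grade 4 applies to QT/QTcF of at least "501 or > 60 ms change from baseline] and [Torsades de pointes or polymorphic ventricular tachycardia, or signs/symptoms of serious arrhythmia". A baseline of 419 ms with a 61 ms rise gives 419 + 61 = 480 ms, so Grade 4 can occur below the threshold. Table 6-5 already requires discontinuation of ribociclib in that case, whatever 7.2.2.6.1 says.
- **A gap for leuprolide.** Table 14-2 lists it as a possible QT risk. Table 6-5 already requires a review of QT-prolonging medication, and Sections 6.4.2 and 6.4.4 address possible-risk drugs. It is arguable whether a study drug counts as concomitant, but that is a missing detail and not a contradiction.

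**Conclusion.** Wrong as written, minor. The conflict over which drugs are stopped is established from the text. The conflict at QTcF 450–480 ms rests on reading the undefined trigger literally, which the wording permits.

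The impact is confined to patients who meet the trigger. For the QTcF part that is about 107 patients, if the 3.3% rate from the earlier trial applies to this broader population. No effect on ribociclib interruption counts arises at 481 ms or more. Between 450 and 480 ms a literal reading could add interruptions, but the documents give no basis for a number. No effect on the primary endpoint is claimed, and no letrozole dose-intensity figure can be supported.

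Timing limits the point further. Amendment 04 records that the Core Phase was complete and that 415 patients had moved to the Extension Phase. Table 7-2 schedules no ECGs there, so only unscheduled tracings could still bring the rule into play.

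**What to change.** In Protocol 7.2.2.6.1 make two substitutions:

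1. Change the action to: *ribociclib must be interrupted*.
2. Replace the abnormal-ECG trigger with: *clinically significant ECG abnormality as judged by the investigator (QTcF 450–480 ms alone is managed as Table 6-5 Grade 1)*.

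Keep the 481 ms threshold, the repeat ECG and the reference to Table 6-5. The second substitution uses a standard that the same section already applies to recording ECG findings. It keeps a trigger for important abnormalities other than QTcF; deleting the phrase, or limiting it to Grade 4, would narrow a mandatory safety rule.

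Do not add a general statement that leuprolide continues. That would set a clinical rule at every QTcF level for a drug listed in Table 14-2, and the documents do not show that the sponsor intends it.

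The cost is one sentence, with no new data, visits or analyses. The planned dose listing with reasons (SAP 2.4.1) and the interruption summaries by component (SAP 2.4.1.5) already show any interruptions of letrozole or the LHRH agonist.

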7.2.3 Patient reported outcomes

The FACT-B will be used to explore patient-reported outcome measures of health-related quality-of-life, functioning, disease symptoms and treatment-related side effects in selected countries including United States, Canada, United Kingdom, France, Italy and Spain. The FACT-B (Brady MJ 1997) is a recognized, reliable and valid instrument frequently used in clinical trials of patients with advanced or metastatic breast cancer.

Due to the nature of the questionnaire and validation, only females will be asked to complete this questionnaire.

Confidential

The FACT-B quality of life questionnaire (see Appendix 14.2) will be administered at study site before any study drug administrations at the visits indicated in Table 7-1 and Table 7-6 utilizing electronic device for data collection. Collection of the FACT-B PRO has up to -3 day window unless otherwise indicated.

All questionnaires should be administered in the patient's local language at the beginning of the study visit prior to any interaction with the study investigator to avoid biasing the patient's perspective. This is to avoid potentially biasing patients or their responses to study questionnaires. Patients should be given sufficient space and time to complete the study questionnaire and the administered questionnaire should be reviewed for completeness. If missing responses are noted, patients should be encouraged to complete any missing responses. Attempts should be made to collect responses to the questionnaire for all patients, including from those who discontinue prior to the study evaluation completion visit, however, if patients refuse to complete the questionnaire, this should be documented in study source records. A patient's refusal to complete the study questionnaire is not considered a protocol deviation.

Completed questionnaires, including both responses to the questions and any unsolicited comments written by the patient, must be reviewed and assessed by the investigator before the clinical examination for responses which may indicate potential AEs or SAEs. This review should be documented in study source records.

If an AE or SAE is confirmed then the physician should record the event as instructed in Section 8 of this protocol. Investigators should not encourage the patients to change responses reported in questionnaires.

Patient Questionnaires	Cycle	Day	Time
FACT-B	Cycles 1 to 6	Every cycle during the first 6 cycles	At the beginning of the
	Cycle 7 and subsequent cycles	Every 2 cycles: Cycle 8,10,12 Every 3 cycles after that: 15, 18, etc.	study visit prior to any interaction with the study investigation.
	End of treatment	Day of end of treatment assessment	

Table 7-6Patient reported outcomes collection plan

8 Safety monitoring and reporting

8.1 Adverse events

8.1.1 Definitions and reporting

An adverse event is defined as the appearance of (or worsening of any pre-existing) undesirable sign(s), symptom(s), or medical condition(s) that occur after patient's signed informed consent has been obtained.

Abnormal laboratory values or test results occurring after informed consent constitute adverse events only if they induce clinical signs or symptoms, are considered clinically significant,

require therapy (e.g., hematologic abnormality that requires transfusion or hematological stem cell support), or require changes in study medication(s).

Adverse events that begin or worsen after informed consent should be recorded in the Adverse Events eCRF. Conditions that were already present at the time of informed consent should be recorded in the Medical History page of the patient's eCRF. Adverse event monitoring should be continued for at least 30 days (or 5 half-lives, whichever is longer) following the last dose of study treatment. Adverse events (including lab abnormalities that constitute AEs) should be described using a diagnosis whenever possible, rather than individual underlying signs and symptoms. When a clear diagnosis cannot be identified, each sign or symptom should be reported as a separate Adverse Event.

Adverse events will be assessed and graded according to the Common Terminology Criteria for Adverse Events (CTCAE) version 4.03. Grade 1 to 5 will be used to characterize the severity of the Adverse Event.

If CTCAE grading does not exist for an adverse event, the severity of mild, moderate, severe, and life-threatening, death related to the AE corresponding to Grades 1 - 5, will be used. Information about any deaths (related to an Adverse Event or not) will also be collected though a Death form.

The occurrence of adverse events should be sought by non-directive questioning of the patient (subject) during the screening process after signing informed consent and at each visit during the study. Adverse events also may be detected when they are volunteered by the patient (subject) during the screening process or between visits, or through physical examination, laboratory test, or other assessments. As far as possible, each adverse event should be evaluated to determine:

- 1. The severity grade (CTCAE Grade 1-5)
- 2. Its duration (Start and end dates)
- 3. Its relationship to the study treatment (Reasonable possibility that AE is related: No, Yes, investigational treatment, Yes, the study treatment (non-investigational), Yes, both and/or indistinguishable)
- 4. Action taken with respect to study or investigational treatment (none, dose adjusted, temporarily interrupted, permanently discontinued, unknown, not applicable)
- 5. Whether medication or therapy was given (no concomitant medication/non-drug therapy, concomitant medication/non-drug therapy)
- 6. Whether it is serious, where a serious adverse event (SAE) is defined as in Section 8.2.1 and which seriousness criteria have been met.
- 7. Outcome (not recovered/not resolved, recovered/resolved, recovering/resolving, recovered/resolved with sequalae, fatal, unknown).

If the event worsens the event should be reported a second time in the eCRF noting the start date when the event worsens in toxicity. For grade 3 and 4 adverse events only, if improvement to a lower grade is determined a new entry for this event should be reported in the eCRF noting the start date when the event improved from having been Grade 3 or Grade 4.

All adverse events should be treated appropriately. If a concomitant medication or non-drug therapy is given, this action should be recorded on the Adverse Event eCRF.

Once an adverse event is detected, it should be followed until its resolution or until it is judged to be permanent, and assessment should be made at each visit (or more frequently, if necessary) of any changes in severity, the suspected relationship to the study treatment, the interventions required to treat it, and the outcome.

Progression of malignancy (including fatal outcomes), if documented by use of appropriate method (for example, as per RECIST criteria for solid tumors or as per Cheson's guidelines for hematological malignancies), should not be reported as a serious adverse event.

Adverse events separate from the progression of malignancy (example, deep vein thrombosis at the time of progression or hemoptysis concurrent with finding of disease progression) will be reported as per usual guidelines used for such events with proper attribution regarding relatedness to the drug.

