10.5.3.2 Adverse events (AEs)

Summary tables for adverse events (AEs) will include only AEs that started or worsened during the on-treatment period, the *treatment-emergent* AEs.

The treatment-emergent adverse events (new or worsening from baseline) will be summarized by system organ class and or preferred term, severity (based on CTCAE grades), type of adverse event, relation to study treatment

Serious adverse events, non-serious adverse events and adverse events of special interest (AESI) during the on-treatment period will be tabulated.

All deaths (on-treatment and post-treatment) will be summarized.

All AEs, deaths and serious adverse events (including those from the pre and post-treatment periods) will be listed and those collected during the pre-treatment and post-treatment period will be flagged.

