#### 2. on-treatment period:

Core Phase: For patients who discontinue after the Core Phase treatment, on-treatment period is defined as from date of first administration of study treatment to 30 days after date of last actual administration of any study treatment (including start and stop date). For patients who transition to the Extension Phase, on-treatment period is defined as from date of first administration of study treatment to the date of last actual administration of study treatment to the date of last actual administration of study treatment to the date of last actual administration of study treatment to the date of last actual administration of study treatment to the date of last actual administration of any study treatment in the Core Phase.

Extension Phase: from date after the first administration of study treatment in the Extension Phase to 30 days after date of last actual administration of any study treatment

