#### 3. *post-treatment period*:

Core Phase: starting at day 31after last administration of study treatment for patients who discontinue after the Core Phase treatment without transitioning to the Extension Phase. Post-treatment period is not applicable for patients who transition to Extension Phase.

Extension Phase: starting at day 31 after last administration of study treatment in the Extension Phase.

Safety summaries (tables, figures) include only data from the on-treatment period with the exception of baseline data which will also be summarized where appropriate (e.g. change from baseline summaries). In addition, a separate summary for death including on treatment and post treatment deaths will be provided. In particular, summary tables for adverse events (AEs) will summarize only on-treatment events, with a start date during the on-treatment period (*treatment-emergent* AEs).

However, all safety data (including those from the post-treatment period) will be listed and those collected during the pre-treatment and post-treatment period will be flagged.

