## 2.8.6 Safety during Extension Phase

Safety analyses for the Extension Phase will be performed on the Safety Set in Extension Phase. The assessment of safety will be based mainly on the frequency of AEs and SAEs. The following summaries will be provided:

- Adverse events (refer to Section 2.8.1)
- Adverse events of special interest (refer to Section 2.8.2)
- Deaths (refer to Section 2.8.3)

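### The SAP defines treatment-emergent AEs by record start date alone, so a Core Phase grade 3/4 event that improves during the Extension is counted as a new Extension AE

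*Protocol*

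**What the plan says.** Protocol 8.1.1 splits one event into several eCRF records as its grade changes. A worsening event is entered again from the date it worsened. For grade 3 and 4 events only, a fall to a lower grade is also re-entered: "a new entry for this event should be reported in the eCRF noting the start date when the event improved".

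On the analysis side the two documents differ. Protocol 10.5.3.2 states that the AE tables "will include only AEs that started or worsened during the on-treatment period", and it adds a comparison with baseline: "The treatment-emergent adverse events (new or worsening from baseline) will be summarized". SAP 2.1.3 states that the AE tables "will summarize only on-treatment events, with a start date during the on-treatment period" and sets no condition on grade. SAP 2.8.1 likewise separates on-treatment events from others by start date. SAP section 4 declares no change from the protocol's analyses.

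The Extension is a separate counting period. SAP 2.1.3 gives it its own on-treatment window, beginning "Extension Phase: from date after the first administration of study treatment in the Extension" Phase. SAP 2.8.6 adds: "Safety analyses for the Extension Phase will be performed on the Safety Set in Extension Phase". For AEs, events of special interest and deaths it refers back to the Core Phase rules in 2.8.1 to 2.8.3.

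**The concern.** A rule based on start date cannot tell a record that marks worsening from one that marks recovery, because both carry a new date. At a period boundary this matters. The parent record starts in the Core Phase, the improvement record starts in the Extension, and only the second falls in the Extension window. The patient has got better, and the table shows an Extension AE.

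The frequency and severity of AEs and SAEs in the Extension is a named secondary endpoint (Protocol Table 3-1, SAP Table 1-1), meant to describe long-term safety. Recovery from older toxicity would be reported as late toxicity.

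No stated SAP rule removes these records. Counting each patient once per category and at maximum grade (SAP 2.8.1) works within one summary, with nothing to link an Extension record to its Core predecessor. The rule requiring a gap of more than one day between records is stated only for the SAE occurrence summary.

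**Working it through.** The plan gives no figure for this quantity, so there is none to reproduce. The check applies both definitions to the same records and then sizes the effect per patient.

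**Step 1: one improving event, with assumed dates.** First Extension dose: 20 Oct 2019. Record A: grade 3, 20 Sep to 19 Nov 2019. Record B, same preferred term: grade 1, from 20 Nov 2019, created by the Protocol 8.1.1 improvement rule.

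- SAP rule (start date in the Extension window): A is out because 20 Sep precedes 20 Oct; B is in. Count = 1.
- Protocol rule (started or worsened, relative to baseline): B continues A, and grade 1 is below grade 3. Count = 0.
- Gap between the end of A and the start of B: 1 day. That is not more than 1 day, so the SAP's own occurrence rule would treat A and B as one occurrence. That rule is not applied to the incidence tables.

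**Step 2: neighbouring cases.**

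| Event across the boundary | SAP rule | Protocol rule |
|---|---|---|
| Grade 3 in Core, grade 1 in Extension | 1 | 0 |
| Grade 2 in Core, grade 3 in Extension | 1 | 1 |
| Resolved in Core, new episode in Extension | 1 | 1 |
| Grade 3 in Core, resolves outright in Extension (end date only, no new record) | 0 | 0 |

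The definitions part only in the first row: improvement to a lower, non-zero grade.

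**Step 3: which tables move.** Record B carries the improved grade. It can therefore add to any-AE, SOC/PT, special-interest and treatment-related counts. It adds to the grade 3/4 count only when grade 4 becomes grade 3. It adds to SAE incidence only if the seriousness flag is carried to the new record.

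**Step 4: size per patient.** The Amendment 04 rationale puts 415 patients in the Extension. A patient whose only Extension record in a category is an improvement record adds 1/415 = 0.24 percentage points to that category. The number of such patients is not in the documents. As an assumed range, 5 patients give 5/415 = 1.20 points and 10 give 10/415 = 2.41 points.

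**Step 5: the Core Phase.** The same mechanism needs a grade 3/4 AE that begins between consent and first dose and improves without resolving after first dose. Protocol 8.1.1 sends conditions already present at consent to Medical History, and screening lasts at most 28 days (Table 7-1).

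**The case against.** The best reply is that the SAP never meant to depart from the protocol. Because worsening creates a new dated record, selecting on start date does implement both starting and worsening, and SAP section 4 says nothing was changed. On this view the baseline comparison in Protocol 10.5.3.2 still governs and the SAP merely lacks a sentence. The first part stands: a reader might infer that the SAP has stopped counting by worsening, and it has not. But a programmer following SAP 2.1.3 as written would include the improvement records, so the stated rule gives a wrong count.

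The second reply is that few such events should be open at transition, and the documents support it. Protocol 4.3 places most pivotal-trial events of special interest early: QTc prolongation in the first 2 cycles, 83.8% of liver enzyme elevations in the first 6 cycles, and 85% of grade 3/4 neutropenia in the first 12 months. The Core Phase ran until 18 months after the last patient's first visit. Tables 6-3 and 6-7 hold or stop ribociclib for many high-grade events, and Protocol 6.3.1 requires discontinuation after a toxicity-related interruption of more than 28 days. If these rules are followed, many improvement records would be dated before the first Extension ribociclib dose.

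Third, the Extension output is descriptive and single-arm, no hypothesis is tested, and all AEs are listed with dates, so the records can be traced. That limits the consequence but does not correct the tables.

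**Conclusion.** The point holds as a specific, undeclared difference between the SAP's counting rule and the protocol's. It affects Extension AE counts for events that were grade 3/4 in the Core Phase, were still open at transition, and later fell to a lower non-zero grade. Each affected patient moves a category by at most 0.24 percentage points, and only if no other Extension record already places that patient in it. The total is unknown and probably small. The 0.24 assumes that all 415 patients are in the Extension Safety Set.

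Three stronger readings are not supported:

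- A reader might take the 59.3% grade 3/4 neutropenia in the pivotal trial (Protocol 1.2.1.2.1) as a sign that many Extension patients are affected. That figure is the share who ever had the event, not the share with it open on the day of transition.
- A reader might infer that severe Extension toxicity is inflated. The added record carries the lower grade, so this happens only for a grade 4 to 3 change.
- A reader might infer that the primary Core Phase endpoint is materially distorted. The only route is the narrow pre-dose case, which should be rare.

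**What to change.** Amend SAP 2.1.3, 2.8.1 and 2.8.6 as follows:

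- Join contiguous records of the same preferred term into one episode, across the boundaries between pre-treatment, Core and Extension periods. The SAP's existing gap rule of more than one day can serve. Joining only contiguous records ensures that a genuinely new episode still counts.
- Count a record as treatment-emergent in a period only if it begins a new episode, or if its grade exceeds the last grade of that episode before the period.
- Keep improvement-only records in the listings.

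One consequence should be stated in the SAP. An event that goes from grade 3 in Core to grade 1 and then grade 2 in the Extension would not count, which follows the protocol's comparison with baseline.

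The cost is SAP wording and programming. The dates, grades and preferred terms are already collected, so no new data are needed.
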